Remote Ischemic Conditioning (RIC) to Decrease Postoperative Complications After Major Abdominal Surgery - A Phase IIa Trial

NCT03234543

09/08/2017

I. STUDY TITLE: Remote Ischemic Conditioning (RIC) to Decrease Postoperative Complications After Major Abdominal Surgery - A Phase IIa Trial

II: STUDY GOALS AND OBJECTIVES:

1. To obtain preliminary data regarding postoperative complications in subjects undergoing abdominal surgery and receiving remote limb ischemic or sham conditioning.

Subjects undergoing abdominal surgery will be prospectively randomized in equal proportions to receive either remote or sham lower limb ischemic conditioning immediately before surgery commences and on postoperative days 1 and 2. Each intervention will comprise 3 cycles of 5/5 minutes of inflation/deflation of a pneumatic cuff on mid-thigh. Postoperative complications within 30 days after surgery will be evaluated using Comprehensive Complication Index (CCI)¹, a continuous, scaled (0-100) and a validated measure of the total complications burden.

The preliminary data is expected to help in determining whether larger trials of RIC to decrease postoperative complications should be pursued, and provide more reliable estimates of CCI without and with RIC, sample sizes and power in design of larger trials.

2. To test whether remote limb ischemic conditioning (RIC) decreases systemic inflammatory response in patients undergoing major abdominal surgery.

Time-dependent differences between the two groups in plasma levels of inflammatory cytokines (TNF-a, IL - 1β , 6, 8 and 10), acute phase proteins (C reactive protein [CRP], alpha-1-acid glycoprotein, fibrinogen [FGN], and haptoglobin) complement components (C2, C4b, C5, C5a, and C5b-9), and blood leukocyte gene expression at baseline and one hour after completion of surgery and the second and third interventions will be tested for significance. It is hypothesized that RIC would decrease systemic inflammatory response to major surgery.

III: BACKGROUND:

Major abdominal surgery is associated with a high risk of post-operative complications. Up to 16.4% of all general surgery patients may have at least one complication. This proportion increases with the complexity of the surgery.² More severe complications are associated with death and longer hospital stay.² One of the common pathways contributory to an increase in complications is excessive systemic inflammation in response to the stress of surgery. In one study, plasma levels of C-reactive protein (CRP), an acute-phase reactant and marker of inflammation, as well as interleukin (IL) 6 (a known pro-inflammatory cytokine), were increased in trauma patients with multi-organ dysfunction syndrome (MODS) compared to those without organ dysfunction.³ By contrast, levels of IL-10, an anti-inflammatory cytokine, were decreased in patients with MODS.³ Another study confirmed these findings in major abdominal surgery; plasma levels of pro-inflammatory cytokines IL-6 and IL-8 were increased, although levels of the

anti-inflammatory cytokine IL-10 were also increased.⁴ This study and another by the same group also showed activation of the complement cascade with surgery, both via the classical and alternate pathways.^{4,5} Thus, major abdominal surgery induces significant changes in the innate immune system, changes that may be excessive and may contribute to complications after surgery in some patients.

Remote ischemic conditioning (RIC) is an innate biological phenomenon wherein a brief ischemic stimulus in an organ or tissue such as skeletal muscle induces protection in remote/distant organs against ischemia and other noxious stimuli. This effect can be induced by repeated and intermittent inflation of a pneumatic tourniquet or a blood pressure cuff on a leg or arm for 5-10 minutes for 3 or 4 times to a pressure adequate to occlude arterial flow interspersed with deflation of 5 minutes. RIC has been applied in many contexts in animal models. In rabbits, femoral artery occlusion-induced ischemia was shown to be protective against myocardial infarction following coronary occlusion.⁶ In a mouse model of resuscitation from hemorrhagic shock, RIC prevented liver and lung injury; this study showed that ischemic conditioning was beneficial when applied before or after the induction of shock. However, the protective effect from postconditioning was less than that from preconditioning.⁷ Other groups have shown in healthy volunteers that RIC induces anti-inflammatory effects, including modulation of blood leukocyte gene expression,⁸ decrease in complement C3 expression,⁹ and a decrease in overall inflammation by multiple other pathways.¹⁰

Translation of RIC to clinical practice has been met with mixed success. Intra-operative RIC induced via 10-minute cycles of iliac artery clamping was shown to provide myocardial and renal protection in patients undergoing open repair of abdominal aortic aneurysm.¹¹ RIC applied daily over a long period of time may be beneficial in reducing the rate of strokes in patients with intracranial arterial stenosis.¹² Finally, preoperative RIC was shown to decrease acute kidney injury (AKI) in subjects undergoing major cardiac surgery.¹³ However, in two larger trials in cardiac surgery, RIC failed to show any differences in several clinical outcomes.^{14,15} It is possible that the use of propofol may have blunted the effect of RIC in these latter studies. Thus, the role of RIC in surgical patients is unclear. It is noteworthy that in most of the trials in surgical patients the RIC stimulus was applied only preoperatively.

Recently, this group of investigators commenced an evaluation of remote ischemic conditioning in combined pre and postoperative settings. It is based on the premise that ischemic preconditioning only, especially when applied only once and immediately before commencement of surgery, may not induce a strong enough biological protective response. Furthermore, it is postulated that a combination of pre-and postconditioning extending into the postoperative period is more likely to provide a stronger beneficial effects. Recently, the investigators completed a pilot study to examine feasibility and tolerance of lower limb ischemic conditioning pre and postoperatively (a total of five applications) in liver transplant recipients. A majority of patients tolerated all four postoperative interventions. The current study aims to apply the RIC stimulus in patients undergoing major abdominal surgery, and test whether RIC decreases inflammatory response following major abdominal surgery.

IV. STUDY HYPOTHESIS:

The central hypothesis of the research is that pre- and post-operative RIC in patients undergoing major abdominal surgery would decrease the systemic inflammatory response to major abdominal surgery and decrease postoperative complications.

V. STUDY DESIGN:

A prospective, randomized, double – masked clinical trial of RIC will be conducted in adult patients undergoing major abdominal surgery at University Hospital (UH) in Newark, NJ. Participants will be randomized into two groups: RIC and No RIC. In the RIC group, RIC will be induced at three time points – the first after anesthesia induction but before commencement of surgery, and the second and the third on post-operative days 1 and 2, respectively. The RIC intervention consists of 5 minutes of inflation of a pneumatic tourniquet placed mid-thigh followed by 5 minutes of deflation, repeated for 3 cycles. The pressure used will be 250 mmHg for the pre-operative intervention (a high pressure chosen because of significant variability of patient blood pressures in a recently anesthetized patient). Tourniquet pressures in postoperative interventions will be 50 mmHg above the patient's systolic blood pressure (the blood pressure is expected to be less labile than immediately after anesthesia induction). The No RIC group will receive a sham intervention at time points identical to those in the RIC group. The thigh tourniquet will be inflated to only 20 mmHg (to mask the intervention from the subject). Persistence of arterial flow will be confirmed with Doppler interrogation.

VI. STUDY POPULATION:

Adults (\geq 18 years of age) of both sexes scheduled for elective major abdominal surgery at UH are eligible for inclusion. Major abdominal surgery is defined as surgery expected to last \geq 120 minutes (from incision to closure) with an expected hospital stay \geq 2 days. A list of surgeries considered for inclusion is included as Appendix A. Additional operations will be considered for inclusion if the study team and primary surgical team both agree that the procedure is a major abdominal surgery and that the duration of surgery is likely to be \geq 2 hours.

Inclusion criteria

- 1. Adults (> 18 years of age)
- 2. Both genders

- 3. Undergoing major abdominal surgery as above
- 4. Elective surgeries
- 5. Both outpatients and in-hospital patients
- 6. Post-op length of stay expected to be at least 2 days by the primary surgical service

Exclusion Criteria

- 1. Subjects with lower extremity paralysis
- 2. Lower extremity amputees
- 3. Known, documented peripheral arterial disease
- 4. Body mass index > 45
- 5. Pregnancy
- 6. Trauma patients
- 7. Organ transplant recipients
- 8. Prior major surgery during current hospitalization (for instance, a patient undergoing relaparotomy for a complication from a previous procedure)
- Patient taking sulfonylureas or nitrates prior to or during admission (listed in Appendix B)
 - a. These subjects are excluded because sulfonylureas are shown to abrogate the RIC effect whereas nitrates are shown to mimic the RIC effect in animal models.
- 10. Non-elective surgeries (urgent or emergent surgeries)
- 11. General surgical procedures with no planned intra-abdominal component

VII. RESEARCH METHODS:

VII.1 Recruitment and enrollment: Eligible candidates for participation will be identified by communication with the general surgery house staff and attendings. Outpatients and inpatients at University Hospital in Newark, NJ will be screened. Outpatients will be approached for study participation either in the outpatient office or in UH on the morning of surgery. Inpatients will be approached for study participation, either the day before or on the morning of the surgery.

VII.2 Randomization: Eligible and consenting subjects will be enrolled and randomized. A randomization table was created using a table of random numbers to assign subjects to RIPC and No RIPC groups. Subjects will be randomized in blocks of 6 to ensure equal randomization into the two groups. The randomization table has been entered into the REDCAPs program. After enrollment, the research team member who will conduct the intervention will access the REDCAPS program online immediately before the induction of anesthesia and obtain group assignment. **VII.3 Masking:** The study will be conducted in a double-masked fashion. Investigative team member/s that will carry out randomization and administer the intervention will not be involved in evaluation of clinical and laboratory outcomes. The primary surgical team, nurses, and any consulting services caring for the patient will be unaware of the group assignment. Other care providers will not be informed of the group assignment. Outcome assessors will not be involved in randomization and administration of the RIC intervention. Adequate steps are in place to mask the outcome assessors (clinical and laboratory) from knowing group assignment.

Subjects will be masked from recognizing which group they are in in the following manner: a) Subjects will not be informed of the group assignment throughout their participation in the study; b) subjects randomized to No RIPC will have a tourniquet placed on the thigh and inflated. It is anticipated that the subject is likely to perceive the inflation as the true RIPC. No information will be provided to subjects regarding the amount of pressure used to inflate the tourniquet in either group.

VII.4 RIC Intervention and Perioperative Care: Sham and RIC interventions will be as described above in section V. All other aspects of anesthesia care will be as per standards of practice. All aspects of the surgical procedure and postoperative care including decisions regarding discharge will be as per standards of practice. The diagnosis and treatment of complications will be under the purview of the clinical care team. The research team will not participate in the clinical care of the subjects.

VII.5 Blood Sample Collection and Processing: Ten mL of venous blood (10mL) will be collected at baseline, an hour after completion of skin closure, and an hour after completion of second and third RIC interventions. 2.5 mL will be placed in PAXgene Blood RNA tubes (Qiagen) for RNA isolation from leukocytes. RNA will be submitted to our Molecular Resource Facility for RNA sequencing. Remaining blood will be placed in EDTA tubes, centrifuged at 3500 rpm and plasma will be stored in aliquots at -70^oC.

VIII. Outcomes:

VIII.1 Primary Outcome:

The CCI, a validated and scaled score of all surgical complications (range 0 [no complications] to 100 [death]) is the primary outcome.

All complications within 30 days after surgery will be graded as per Clavien-Dindo classification.^{1,2} CCI will be computed for each subject using the publically available website, http://www.assessurgery.com/. Follow up after discharge will occur either in clinic or via telephone

VIII.2 Secondary Clinical Outcomes:

- 1. Proportion of patients in each group that complete all three RIC interventions
- 2. Hospital days

3. 30-day mortality (will be captured as part of CCI)

VIII.3 Secondary Molecular Outcomes:

- 1. Plasma cytokines levels (TNF-a, IL 1β , 6, 8 and 10)
- 2. Plasma acute phase reactant proteins (CRP, alpha-1- acid glycoprotein, FGN, and haptoglobin)
- 3. Plasma complement levels (C2, C4b, C5, C5a, and C5b-9)
- 4. Peripheral blood leukocyte gene expression profiles determined by RNA sequencing.

Commercially available kits will be used for the plasma assays in section VIII.3.

IX. Data Collection and Analysis:

IX.1 Data Collection, and Study Variables

Data regarding subject screening for eligibility, recruitment, and enrollment will be stored in an Excel file on a dedicated Rutgers server with password protection. Other data will be entered electronically into case report forms via the online REDCaps software. Hard copy case report forms are also available as needed to facilitate the transfer of data to online software.

IX.2 Case Report Forms (CRFs)

5 CRFs will be used to collect study-related data as follows.

- CRF 1 will capture baseline characteristics. Variables collected will include age, sex, ethnicity, height, weight, baseline medical characteristics, length of hospital stay, baseline laboratory values, and care needs at the time of surgery (whether hospitalized, in ICU, etc).
- CRF 2 will capture operative information. Variables will include the type of surgery, date, time, and duration of surgery, blood loss and fluid replacement.
- CRF 3 will capture intervention-related data, including time of intervention, patient's systolic blood pressure and tourniquet pressure used, patient's pain scale as a result of the intervention, and whether or not the intervention was completed.
- CRF 4 will capture complication related data. All post-op complications will be graded I V according to the Clavien-Dindo grading scale.² The number of each type of complications will be recorded. This data will be used to calculate CCI using an online calculator available at www.assesssurgery.com.¹
- CRF 5 will capture data related to the molecular studies as discussed previously.

IX.3 Data Analyses

Methods of proposed data analyses are described in the Statistical analyses plan section, Appendix C.

X. Risks and Benefits

X.1 Risks to Subjects

In an awake patient (post-op), tourniquet inflation may cause pain. The investigators expect that the risk of pain overall is small. In a recently concluded pilot study of RIC in liver transplant recipients, a majority of subjects completed all four postoperative RIC interventions. The investigators anticipate that the proportion of subjects that would complete the two postoperative interventions in the proposed study would be either similar to the liver transplant recipient study or higher (because of 2 instead of 4 postoperative interventions). Importantly, the subjects will have the option to discontinue the research intervention if they perceive the pain as excessive.

There is a theoretical risk of ischemic injury to the limb receiving the RIC stimulus. However, no study using RIC previously has reported any such cases.^{16–18} The investigators did not encounter any ischemic injury from tourniquet inflation in the liver recipient study.

Venipuncture has risks of bleeding and ecchymoses at the venipuncture site. However this risk is expected to be very small and not different from a routine blood draw. The amount of blood drawn for study purposes will be small (less than 50 mL total anticipated) and spread over a period of 3 days, and therefore is not expected to pose any risks to the subjects.

X.2 Benefits to Subjects

The anticipated benefit to subjects is fewer complications after major abdominal surgery. Fewer complications could lead to shorter hospital length of stays and possibly improved quality of life. In addition, the study is expected to provide valuable information regarding how RIC might modulate stress response to major surgery. It may help elucidate the pathways by which RIC modulates inflammation after surgery. If RIC reduces postoperative complications, data from this study would provide support for larger and more definitive studies.

References

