# Appendix C: Statistical Analysis Plan

# I. Introduction

This plan provides a detailed description of the study endpoints, methods of data analyses and other relevant issues pertaining to a prospective randomized controlled trial of remote ischemic conditioning in patients undergoing major abdominal surgery at a single institution.

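### The fixed, disclosed block size of 6 makes some assignments predictable to anyone who has followed the earlier ones, and the plan does not keep such a person out of recruitment

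*Protocol*

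**What the plan says.** Protocol II sets equal allocation: "Subjects undergoing abdominal surgery will be prospectively randomized in equal proportions to receive either remote or sham lower limb ischemic conditioning". Protocol VII.2 gives the method: "Subjects will be randomized in blocks of 6 to ensure equal randomization into the two groups". No other block size and no stratification factor is mentioned. SAP I describes the trial as one of "remote ischemic conditioning in patients undergoing major abdominal surgery at a single institution".

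The table is held in REDCap, and the draw comes late: "After enrollment, the research team member who will conduct the intervention will access the REDCAPS program online immediately before the induction of anesthesia". That team member cannot be masked. Under Protocol V, the pre-operative cuff pressure is 250 mmHg in the RIC group, while for sham "The thigh tourniquet will be inflated to only 20 mmHg (to mask the intervention from the subject".

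Protocol VII.3 separates roles at the outcome end: "Investigative team member/s that will carry out randomization and administer the intervention will not be involved in evaluation of clinical and laboratory outcomes". It also keeps the surgical team, nurses and consulting services unaware of the arm. There is no matching statement for the entry end. VII.1 says that candidates come through the surgical house staff and attendings, but not who approaches or consents them.

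On operations outside the Appendix A list, Protocol VI says: "Additional operations will be considered for inclusion if the study team and primary surgical team both agree".

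SAP V.1 compares CCI between arms with a t test or a Mann-Whitney test, without covariates. Regression is reserved for exploratory interactions.

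**The concern.** Drawing the assignment after enrolment hides the stored table. It does not stop someone who knows the block size from working out the next arm from the previous ones. Once three of either arm have been used, the rest of the block is fixed.

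If that person also has a say in who enters, a borderline patient could be declined when the next arm is the unwanted one. The arms would then differ in baseline risk. Masking of patients, surgeons and assessors guards against differences in care and in assessment, not against this. The primary test makes no adjustment, so the difference would pass into the CCI estimates that the pilot is meant to supply for larger trials.

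**Working it through.** The documents give no predictability figure to reproduce, and SAP VI.4 (sample size and power) gives no sample size. The share per complete block does not depend on the sample size.

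**Inputs.** Block of 6 (Protocol VII.2); equal allocation, hence 3 + 3 per block (Protocol II); one running list (one site and no stratification stated, so this is an inference). There are C(6,3) = 20 equally likely blocks.

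**Assignments that are certain**, for an observer who knows the block size, where the block starts and every earlier assignment in it:
- Positions 1 to 3: never.
- Position 4: first three alike, 2/20 = 10%.
- Position 5: three of one arm among the first four, 2 × C(4,3)/20 = 8/20 = 40%.
- Position 6: always, 100%.

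The sum is 0.1 + 0.4 + 1.0 = 1.5 of 6, or 25.0%. As a check, 12 of the 20 blocks have one certain assignment, 6 have two and 2 have three: (12 + 12 + 6)/20 = 1.5. The range in a single block is 1/6 = 16.7% to 3/6 = 50%.

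**Best guess** (name the arm used less so far, toss a coin if tied). The chance of being right at positions 1 to 6 is 0.5, 0.6, 0.6, 0.7, 0.7 and 1.0. The sum is 4.1, and 4.1/6 = 68.3%, against 50% by chance.

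**Incomplete knowledge.** VII.3 allows for more than one interventionist. Suppose each earlier assignment is seen independently with probability q (an assumption; the documents give nothing on this). Certainty needs all three of the exhausted arm to have been seen, so the certain share is 0.25 × q³:

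| q | Certain share |
|---|---|
| 100% | 25% |
| 75% | 0.25 × 0.422 = 10.5% (10.6% by simulation) |
| 50% | 0.25 × 0.125 = 3.1% |
| 25% | 0.25 × 0.0156 = 0.4% |

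**Varying block sizes.** These figures are simulated, for an observer who knows the set of sizes and every past assignment but not the order of the sizes:

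| Scheme | Certain | Best guess right |
|---|---|---|
| Fixed 6 | 25% | 68.3% |
| Random 4/6 | 5.6% | 69.2% |
| Random 2/4/6 | 4.1% | 70.3% |
| Random 4/6/8 | 2.5% | 68.0% |

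A second simulation of 4/6/8, with lists of 60 subjects (an assumed length) and certainty counted as probability above 0.999, gave 2.3% and 67.8%. Varying the sizes removes most of the certainty but almost none of the better-than-chance guessing.

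**The case against.** The strongest reply is that the route to bias rests on silence. No sentence says that the interventionist screens, approaches or consents anyone. Candidates are identified through the surgical staff, the expected stay is judged by the primary surgical service, and the research team takes no part in clinical care, so nothing gives it control over when surgery takes place. All of this stands: the protocol neither establishes nor rules out that the same person recruits.

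Four stronger readings are tempting, and the documents do not support them.
- *A quarter of all assignments are known in advance.* This holds only on average and for an observer with complete knowledge. The wording of VII.3 leaves room for several interventionists, so complete knowledge is an assumption.
- *The study team alone decides on off-list operations.* Protocol VI and Appendix A require the surgical team's agreement too, and that team is unaware of assignments. The study team could decline such a case but could not admit one alone.
- *No analysis could repair the damage.* Type of surgery and baseline characteristics are collected (Protocol IX.2) and baseline data are summarised by arm (SAP IV). Imbalance in measured factors could be seen and partly adjusted for; unmeasured selection could not.
- *Locking eligibility before release would close the gap.* VII.2 already places the draw after enrolment, and a lock does not prevent prediction from earlier assignments.

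It is also fair to say that fixed blocks are a common choice and that this is a Phase IIa pilot with no power claim. That lowers the severity but does not remove the point, because CCI is still the primary endpoint and is formally tested.

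**Conclusion.** The point holds as a cheap improvement of lower severity. A single disclosed block size, together with an interventionist who knows the arms and is not excluded from recruitment, leaves an opening for selective entry. Its size is at most 25% certain assignments on average, with 68.3% best-guess accuracy. The certain share falls to between 10.5% and 0.4% if only 75% to 25% of earlier assignments are seen.

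These figures assume one unstratified list, complete blocks, and an observer who knows the block size and where each block starts. They measure predictability, not bias. A reader might infer that the CCI comparison will be biased. The documents do not support that: bias also requires the person who can predict to influence entry and to act on it. If that happened, the planned unadjusted test would not correct it.

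**What to change.** 1. Regenerate the unused part of the REDCap list with randomly varying block sizes, for example 4, 6 and 8, and keep the sizes out of the protocol that the study team sees. Certain assignments fall to roughly 2%.
2. Add to VII.2 or VII.3 that, within the existing staff, anyone who knows past assignments takes no part in screening, consent or eligibility decisions, including decisions on off-list operations. This deals with the guessing that varying block sizes leave in place.

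The cost is one new table upload, a sentence or two of protocol text and some care in dividing tasks. The statistical downside is small: if enrolment stops mid-block, the arms can differ by up to half the last block, which is 4 subjects for a block of 8 against 3 for a block of 6.
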